6.2.8. Safety Analyses

All safety analyses will be based on the safety analysis set, as defined in [Section 3.1.3](#). Descriptive statistics will be used to summarize the safety outcomes. The continuous safety variables will be summarized at each visit including end of each cycle (the last non-missing assessment during the cycle), end of treatment (the last non-missing assessment during the applicable treatment period), and end of study (the last non-missing assessment during the whole study), if applicable. No inferential analyses of safety data are planned unless otherwise specified.

6.2.8.1. Chemotherapy Exposure and Compliance Analyses

Duration on treatment and number of cycles will be summarized by treatment. Dose modifications will be summarized for each study drug (trilaciclib, carboplatin, etoposide, or atezolizumab). For each study drug, the dosing endpoints described in [Section 5.2.1](#) will be summarized for the induction treatment period. Atezolizumab specifics summaries will be summarized by maintenance and overall treatment periods as well. This includes the following:

- Number of cycles received;

- Number of missed doses;
- Number of dose reductions;
- Number of dose interruptions;
- Number of patients with missed dose and its reason;
- Number of patients with dose reductions;
- Number of patients with dose interruptions.

The number of cycles delayed and the number and percentage of patients experiencing a treatment cycle delay will be summarized by treatment. The study dosing records and the derived dosing endpoints will be listed.

6.2.8.2. Adverse Events

Number and incidence rates of AEs will be summarized by SOC and/or PT for the following categories of TEAEs: all AEs, SAEs, atezolizumab AESIs, AEs leading to death, and AEs leading to study drug discontinuation or study withdrawal. Patients with more than one occurrence of the same SOC (PT) will be counted only once within the SOC (PT) categorization. AEs and SAEs will be summarized for the induction, maintenance, and overall treatment periods, the rest will be summarized for the overall treatment period only.

AEs will also be summarized similarly by CTCAE grade and relationship to any study drug (trilaciclib, carboplatin, etoposide, or atezolizumab), and by relationship to each drug. Should a patient experience more than one occurrence of the same SOC (PT), the patient's worst occurrence (worst grade/most related causality) will be retained in the tabulation. Those related to any study drug or atezolizumab will be summarized for the induction, maintenance, and overall treatment periods, the rest will be summarized for the overall treatment period only.

All AEs, including AEs that started prior to the study medication, will be presented in patient listings. In addition, separate listings of all SAEs, atezolizumab AESIs, AEs leading to death, drug-related AEs, and AEs leading to study drug discontinuation or study withdrawal will be provided.

The criteria for identifying infusion related reaction AEs or hematologic toxicity AEs are described in [Section 5.2.2](#). A summary table showing the incidence of each category of AEs related to infusion and related to hematologic toxicity will be presented along with its supportive data listing. These will be summarized for the overall treatment period only.

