In summary, nonclinical data demonstrate that trilaciclib administration with chemotherapy preserves bone marrow and immune system function from damage by chemotherapy. Additionally, clinical data from Study G1T28-02 (Section 4.3.1), where patients received trilaciclib or placebo in combination with etoposide/carboplatin, provides compelling evidence that trilaciclib decreases myelosuppression across 3 lineages (neutrophils, RBC, and lymphocytes), and suggests that trilaciclib contributes to a more functional activated immune system as compared with placebo. It is this difference that is hypothesized to translate into potentially improved efficacy (eg, OS) when chemotherapy is combined with checkpoint inhibitors.

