### 13.6. Safety Analyses

Summaries of safety data will be performed using the safety analysis set. Adverse event data will be coded to system organ class and preferred term using MedDRA (Version 17.1 or later). A detailed definition of treatment emergence will be provided in the SAP. The number and percentage of patients experiencing any treatment emergent AEs (TEAE) overall, and by system organ class and preferred term will be tabulated. Adverse events related to treatment will be further summarized by the treatment to which it is attributed (eg, trilaciclib, carboplatin, etoposide, or atezolizumab). Severity will be tabulated based on greatest severity observed for each patient. In analyses of grade and causality, if the same AE occurs on multiple occasions, the highest grade and strongest relationship to study drug will be summarized. Infusion-related reactions (IRRs), AEs leading to study drug discontinuation, use of concomitant medications to treat AEs, as well as incidence and severity of AEs of special interest (AESI) for atezolizumab will be tabulated separately.

Observed values and change from baseline in vital signs, ECG intervals, and hematology, clinical chemistry, urinalysis, and liver function parameters will be tabulated at each visit, as

appropriate. Toxicity grades for clinical lab parameters (eg, hematology, chemistry) will be characterized according to CTCAE, Version 4.03, when possible. Shifts in toxicity grades from baseline to each visit, and from baseline to the worst grade during the study will be summarized. Summaries examining maximum and minimum post-baseline changes will consider both scheduled and unscheduled data.

Graphical presentations of safety data will be presented as is deemed appropriate. This may include, but is not restricted to, presentation of parameters against time, concentration or shift plots. Dose modifications, interruptions, compliance, and patient exposure will be summarized for each study therapy component, where appropriate. This will include, but not limited to the following:

- Occurrence of chemotherapy delays and interruptions
- Occurrence of trilaciclib dose delays and interruptions
- Occurrence of atezolizumab dose delays and interruptions
- Relative dose intensity of carboplatin and etoposide

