2.3. Number of Patients

Overall, approximately 100 patients will be enrolled in the study. The 100 patients will be randomly assigned (1:1 fashion) to trilaciclib 240 mg/m² or placebo administered IV on Days 1 to 3 with E/P/A therapy for up to four 21-day cycles (induction part).

The initial sample size calculations were based on a primary endpoint of OS where a sample size of 100 (1:1 treatment allocation ratio between the two groups of placebo + E/P/A and trilaciclib + E/P/A) provided 80% power to detect a hazard ratio of 0.6 using an overall type 1 error probability of 0.1 (1-sided). With the change in endpoints outlined in amendment 2, the sample size calculation is now based on demonstrating the superiority of trilaciclib + E/P/A versus placebo + E/P/A with respect to at least one of the primary endpoints. With this amendment, the overall type I error rate is now 0.025 (1-sided) and the type II error rate used to compute sample size is 0.10 (corresponding to 90% power).

To maintain the overall type I error rate, by using the most conservative Bonferroni procedure for the 2 primary endpoints, a 1-sided individualized type I error rate $0.025/2 = 0.0125$ is assigned to each outcome variable in the sample size calculation. Assuming a common standard deviation of 2.5, a true difference in the duration of severe (Grade 4) neutropenia in Cycle 1 of at least 2 days between the treatment groups (trilaciclib + E/P/A versus placebo + E/P/A) requires 82 evaluable patients (41 per treatment arm). This implies that 88 patients need to be randomized assuming a 95% evaluability rate. For occurrence endpoints (occurrence of severe (Grade 4) neutropenia, assuming its proportion of 45% for placebo + E/P/A, testing for an absolute reduction of 34% to 11% with trilaciclib + E/P/A would require a sample size of at least 100 patients (50 per treatment arm). Assuming a 95% evaluability rate, at least 106 patients need to be enrolled to complete the study. Therefore, the final adjusted sample size is 106 to account for the evaluation of 2 primary endpoints.

All calculations were carried out using the POWER procedure in SAS® version 9.4.

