5.2.2. Adverse Events (AEs)

All AEs will be coded from verbatim text to PTs and grouped by SOC using the MedDRA Version 20.1. AEs will be collected from the time of signature of informed consent throughout the treatment period and up to 30 days after the last dose of study treatment. SAEs and AESI will be collected through 90 days after the last dose of study drug. AEs are graded by investigator according to CTCAE, Version 4.03.

For the induction treatment period, TEAE analyses will include all AE’s that started on or after the first dose of study drugs and up to the date of first dose of atezolizumab in the maintenance period. If the subject did not enter the maintenance period, then AEs up to the first dose of the last cycle in the induction period + 36 days (inclusive) will be considered TEAE.

For the maintenance treatment period, TEAE analyses will include all AE's that started on or after the first dose of atezolizumab in the maintenance period through the last dose of the maintenance period + 30 days.

For TEAEs that are designated as SAEs or AESIs, data will be summarized through the last dose of atezolizumab + 90 days.

TEAEs will be summarized overall and by the period in which they occur.

Other AE variables include drug-related AEs, AEs leading to study drug discontinuation or study withdrawal, AEs leading to death, SAEs, and atezolizumab AESIs.

AEs with onset/end dates that are partially/completely missing will be imputed as follows:

(i) For onset date:

- If only the day part of the AE onset date is missing and occurs in the same month and year as the first dose date of study drug, the date of first dose of study drug will be used as the onset date of the AE. Otherwise, the first day of the month will be used to complete the onset date of the AE;
- If the day and month parts of the AE onset date are missing and occur in the same year as the first dose of study drug, the date of the first dose of study drug will be used as the onset date of the AE. Otherwise, January 1st will be used to complete the onset date of the AE;
- If the AE onset date is completely missing, the date of the first dose of study drug will be used as the onset date of the AE.

(ii) For end date:

- If only the day part of the AE end date is missing, the last day of the month will be used to complete the end date of the AE;
- If the day and month parts of the AE end date are missing, December 31st will be used to complete the end date of the AE;

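### AESIs, fatal AEs and AEs leading to discontinuation are tabulated only over the whole treatment period as crude percentages, so any difference between arms in time on atezolizumab will look like a difference in harm

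*SAP*

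**What the plan says.** SAP 6.2.8.2 lists five TEAE categories: all AEs, SAEs, atezolizumab AESIs, AEs leading to death, and AEs leading to study drug discontinuation or study withdrawal. It gives the first two by induction, maintenance and overall "periods, the rest will be summarized for the overall treatment period only". AEs related to any study drug or to atezolizumab also get the three-way split. For the infusion-reaction and hematologic AE tables it says: "These will be summarized for the overall treatment period only".

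The measure is a proportion of patients: "Patients with more than one occurrence of the same SOC (PT) will be counted only once within the SOC (PT) categorization". Protocol 13.6 agrees: "The number and percentage of patients experiencing any treatment emergent AEs (TEAE) overall, and by system organ class and preferred term will be tabulated".

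The period has no fixed length. SAP Section 5 runs overall treatment from randomization to the end of the last cycle received. Under SAP Criteria for Subsequent Cycles and Study Duration, atezolizumab stops at progression, toxicity, withdrawal of consent or investigator decision, and may continue past RECIST progression while benefit persists. SAP 5.2.2 adds 30 days for AEs, and for the others: "For TEAEs that are designated as SAEs or AESIs, data will be summarized through the last dose of atezolizumab + 90 days". Randomized treatment covers at most four induction cycles. After that both arms receive the same atezolizumab monotherapy.

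SAP 5.2.2 also says that TEAEs are shown both overall and split by period. That does not agree with the restriction in 6.2.8.2.

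**The concern.** Protocol Table 5-1 names AESIs, infusion-related reactions and discontinuation because of AEs as safety endpoints for trilaciclib or placebo with E/P/A. A reader will put the two percentages side by side. They compare like with like only if the arms were observed for similar lengths of time, and the plan does not secure that.

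A difference in treatment time is plausible. Protocol 4.2 says of the more active immune system seen with trilaciclib: "It is this difference that is hypothesized to translate into potentially improved efficacy (eg, OS) when chemotherapy is combined with checkpoint inhibitors". The difference could also go the other way, if one arm stops earlier for toxicity.

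AESIs are the most exposed category because they keep accruing. Protocol Table 4-1 gives median onsets of 3.5 months (pneumonitis, hyperthyroidism), 4 months (colitis), 5.5 months (hypothyroidism, pancreatitis) and 5.7 months (adrenal insufficiency). All lie beyond a 12-week induction (about 2.76 months). Hepatitis, at 1.1 months, is the exception.

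The SAP already handles unequal follow-up elsewhere. Its models for severe neutropenia, transfusions, dose reductions, MAHE and infection SAEs carry an offset for cycles or weeks (6.2.7.1.1, 6.2.7.1.2, 6.2.7.2.1, 6.2.7.2.5). Those all sit within induction, where duration varies less than over the whole treatment period.

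**Working it through.** **Where the 0.6 comes from.** The plan gives no safety figure to reproduce. The one borrowed figure is the former OS design in SAP 2.3, which "provided 80% power to detect a hazard ratio of 0.6" at one-sided alpha 0.1. Schoenfeld: 4 × (1.2816 + 0.8416)² / (ln 0.6)² = 4 × 4.508 / 0.2609 = 69.1, so 70 deaths. That matches 100 patients followed to 70% deaths, which confirms it as a survival value. Applying it to time on treatment is an assumption.

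**Inputs from the documents.** Reporting window w = 3 months after the last dose for AESIs and SAEs, 1 month for other AEs (SAP 5.2.2). Accrual 12 months and follow-up 24 months (SAP Criteria for Subsequent Cycles and Study Duration). First analysis once all patients could have had 12 weeks of treatment (SAP 6.2.13).

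**Assumed.** Time on treatment T is exponential with rate μ and control median 4, 5 or 6 months. The documents give no PFS or treatment-duration figure. The hazard ratio (HR) for stopping treatment is 1, 0.8 or 0.6. The event hazard λ is constant and the same in both arms.

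**Simple closed form.** Crude incidence = 1 − exp(−λw) × μ/(μ + λ). Take a median of 5 months, w = 3, and λ set to give 20% on placebo.

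- Placebo: μ = ln 2 / 5 = 0.1386 and λ = 0.02307. Then 1 − 0.9331 × 0.1386/0.1617 = 20.0%.
- Longer-treated arm at HR 0.6: μ = 0.0832. Then 1 − 0.9331 × 0.0832/0.1063 = 26.9%.

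Over medians of 4 to 6 months, 20% becomes 26.5% to 27.3% at HR 0.6 and 22.6% to 22.9% at HR 0.8. With w = 1 month the figures are 28.2% to 28.6% and 23.3% to 23.4%.

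**Mature cumulative data.** Limit T to between 0.7 and 24 months. The mean AESI window is 0.7 + (e^(−0.7μ) − e^(−24μ))/μ + 3. At a median of 4 months on placebo (μ = 0.1733) this is 0.7 + (0.8858 − 0.0156)/0.1733 + 3 = 8.7 months. Over the three medians it is 8.7 to 11.1 months on placebo and 11.8 to 14.7 months at HR 0.6. Crude incidence is the average of 1 − exp(−λ(T + 3)), taken at λ = 0.01 and 0.03 per month.

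**First planned cut.** Same model, with the window replaced by the smaller of T + 3 and time since entry. Time since entry is uniform from 3 to 15 months (12 months of accrual, cut about 3 months after the last patient).

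| HR for stopping treatment | Spurious AESI ratio, mature data | First planned cut |
|---|---|---|
| 1.0 | 1.00 | 1.00 |
| 0.8 | about 1.11–1.13 | about 1.04–1.05 |
| 0.6 | about 1.25–1.33 | about 1.08–1.11 |

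Swapping the arms inverts the ratio.

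**Effect of the remedies.** With equal hazards, first events divided by time at risk estimate λ in both arms, so the rate ratio is 1.00 by construction. An induction-only window of c = 2.76 months gives λ/(μ + λ) × (1 − e^(−(μ+λ)c)). In the 5-month example that is 0.1427 × 0.3600 = 5.1% on placebo and 0.2171 × 0.2542 = 5.5% at HR 0.6. The gap almost closes, but most AESIs are then out of view.

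**The case against.** Much of the content is already available by period. All AEs and SAEs are tabulated by SOC and/or PT for induction and maintenance. Where these tables go to PT level, neutropenia, anaemia, thrombocytopenia, febrile neutropenia and infusion-related reaction appear there as terms. Laboratory Grade 3/4 hematologic toxicity has an induction-only analysis with a cycle offset (SAP 6.2.7.2.5). Infusion reactions are linked to the administration forms, and trilaciclib is given only in induction, so its reactions are unlikely to be hidden by maintenance events. Fatal events are SAEs, so they fall within the by-period SAE tables, though not flagged as fatal. Safety is descriptive (SAP 6.2.8), and treatment duration is shown by arm (SAP 6.2.8.1).

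This stands for the hematologic and infusion-reaction tables, which are the weaker part of the point. It does not cover AESIs as a group, fatal AEs as a group, or AEs leading to discontinuation or withdrawal, because a PT table shows none of these groupings. Reporting duration separately lets a reader suspect a distortion but not correct it. Descriptive tables are still compared across arms.

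A reader might infer two stronger things that the documents do not support. One is that the period closes at progression. It closes with study treatment, for any of several reasons, and treatment past progression is allowed. The other is that trilaciclib will therefore look more toxic. No effect on PFS or treatment duration is assumed anywhere, Protocol 4.2 speaks only of potentially improved efficacy, and the sign depends on which arm stays on atezolizumab longer.

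**Conclusion.** The point holds as a conditional one. For AESIs, AEs leading to death, and AEs leading to discontinuation or withdrawal, SAP 6.2.8.2 gives only crude whole-period proportions over a window set by time on atezolizumab. If that time differs between arms, the comparison is distorted towards more apparent harm in the longer-treated arm.

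The distortion is moderate in mature cumulative tables and small at the first cut, as tabulated above. These sizes rest on exponential treatment times, a constant common hazard, assumed control medians of 4 to 6 months, and hazard ratios chosen for illustration. The distortion is nil with equal treatment time, and near nil for events whose risk lies in induction. The efficacy conclusions are untouched.

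A reader might also conclude that the induction table should become the between-arm safety comparison. For AESIs that would be unsound. By the protocol's own onset figures, most would fall outside it, including any delayed immune toxicity of the combination.

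**What to change.** 1. Reconcile SAP 6.2.8.2 with SAP 5.2.2 by tabulating AESIs, AEs leading to death, AEs leading to study drug discontinuation or study withdrawal, infusion-related reactions and hematologic AEs for induction and maintenance as well as overall, using the TEAE periods already defined in 5.2.2.
2. For the overall period, add exposure-adjusted incidence by arm for AESIs, SAEs, AEs leading to death and AEs leading to discontinuation. Define it as patients with a first event per 100 patient-months, counting time from first dose to the first event or the end of the reporting window. Keep the crude percentages beside it.
3. Do not name the induction table as the sole between-arm comparison for AESIs.

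The cost is SAP wording and a few more table columns from dates already collected. Sites and patients are unaffected. The small downside is that exposure-adjusted rates assume a roughly constant hazard, which is a reason to show the period tables alongside them.

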6.2.8.3. Laboratory Evaluations

For hematology and clinical chemistry labs, the observed values and change from baseline will be summarized by cycle visit using descriptive statistics.

Toxicities for clinical labs will be characterized according to CTCAE, Version 4.03 ([Table A-1](#) of Appendix when possible), and the frequency and percentage of patients with each CTCAE grade for each visit during the treatment period will be described. Moreover, any occurrence of grade 3 or grade 4 during the overall treatment period will be summarized, and shift in grade from baseline to the worst post-baseline value will be summarized. Both the scheduled and unscheduled assessments will be used to identify the worst post-baseline values.

Listings of all laboratory data with normal reference ranges, and CTCAE grades (when possible) will be provided.

6.2.8.4. Vital Signs

For vital sign parameters (Systolic Blood Pressure, Diastolic Blood Pressure, Pulse Rate, Temperature, and Weight) the observed values and change from baseline will be summarized using descriptive statistics at each visit during the treatment period.

Additionally, the frequency and percentage of patients with any potentially clinically significant findings (defined in [Table 14](#)) during the overall treatment period will be presented. A listing of all vital sign data will be provided.

6.2.8.5. Performance Status

Descriptive statistics will be presented for ECOG score for the observed values and change from baseline. A listing of ECOG score for all patients will be provided.

6.2.8.6. Physical Examination

A listing of screening physical examination dates for all patients will be provided (where available).

6.2.8.7. ECG

Descriptive statistics will be presented for each ECG parameter for the observed values and change from baseline to post baseline. A listing of all ECG data will be provided.

The criteria for potentially clinically significant findings are defined in [Table 16](#). The frequency and percentage of patients with any potentially clinically significant findings during the induction treatment period will be presented. The supportive data will be provided in patient data listings.

6.2.9. Subgroup Analyses

The MAHE will be examined in the following subgroups:

- Age group (ages <65; >65).
- Gender (Male; Female).
- Brain metastases (Yes; No).
- ECOG performance status (0-1; 2).
- Race (Caucasian; non-Caucasian).
- Region (US; Ex-US).
- Baseline LDH (\leq ULN; $>$ ULN).

Descriptive statistics by treatment group will be presented for each subgroup of patients. Additional subgroups or endpoints may be identified and explored.

6.2.10. Pharmacokinetic Analysis

The PK analysis for a subset of patients will be documented separately and is not covered in this SAP.

6.2.11. Evaluate Genetic and/or Expression (RNA/Protein) Biomarkers in Tumors and Blood

A detailed description of the biomarker analysis plan will be documented separately. In general, as data permits, the analyses may include, but not be limited to:

1. SCLC tumor samples may be assessed for markers of CDK 4/6 dependence and independence (including but not limited to PD-L1, PD-1, and others) as defined by IHC or qRT-PCR on biological/clinical endpoints.
2. SCLC tumor samples may be assessed for markers to potentially predict sensitivity to trilaciclib treatment.
3. Peripheral blood samples may be assessed for biomarkers examining the role of trilaciclib in the preservation of hematopoietic and immune populations during chemotherapy treatment
4. Peripheral blood samples may be assessed for biomarkers examining the role of trilaciclib in anti-tumor immunity

[REDACTED]

